## 1.0 Objectives / Specific Aims

- Aim 1. Assess the incidence of leukopenia in those randomized to maribavir vs. valganciclovir prophylaxis in adult kidney transplant recipients at high-risk of CMV infection.
  - Hypothesis 1. The incidence of clinically meaningful leukopenia, defined as a WBC count of  $< 3,000$  cells/mm^3 and a reduction in total mycophenolate dose below 1,500 mg/day or valganciclovir dose below 900mg per day (adjusted for renal function), will be significantly lower in the maribavir arm, as compared to the valganciclovir arm.
- Aim 2. Assess the efficacy of maribavir vs. valganciclovir prophylaxis in adult kidney transplant recipients at high-risk of CMV infection.
  - Hypothesis 2. The incidence of CMV infection and disease will be similar between the maribavir arm, as compared to the valganciclovir arm, at 3-, 6-, and 12-months post-transplant.
- Aim 3. Assess the impact of maribavir vs. valganciclovir prophylaxis on healthcare utilization and costs in adult kidney transplant recipients at high-risk of CMV infection.
  - Hypothesis 3. Healthcare utilization will be lower in the maribavir arm, as compared to the valganciclovir arm, at 6- and 12-months post-transplant, driven predominantly by reduced number of telephone calls, televisits, and laboratory monitoring encounters.
- Exploratory Aim 4. Assess the impact of maribavir vs. valganciclovir prophylaxis in adult kidney transplant recipients at high-risk of CMV infection on patient-reported outcomes for quality of life and satisfaction.
- Exploratory Aim 5. Assess any differences in leukopenia, efficacy, healthcare utilization and patient reported outcomes by race and sex in patients randomized to maribavir vs. valganciclovir prophylaxis in adult kidney transplant recipients at high-risk of CMV infection.

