### **Efficacy Measures**

10. CMV Infection (Secondary Outcome) – defined as detectable CMV in the patient's plasma. Currently, MUSC uses CMV DNA PCR (plasma IU/mL) to assess for infection with nucleic acid amplification techniques that are calibrated to the WHO international standard for human CMV. The lower level of detection is 50 IU/mL. Per the MUSC CMV protocol and usual care (see Appendix), any level >1,000 IU/mL will be considered CMV infection for the purposes of this study. All cases of CMV infection, regardless of the presence or absence of symptoms, will be classified as infection. CMV DNA PCR is measured at MUSC per our protocol using event-driven criteria, which includes either leukopenia or symptoms consistent with CMV infection (N/V/D, anorexia, fever, chills, and/or malaise). For the purposes of this study, the reason for measuring CMV DNA PCR will be captured and analyzed as well. Further, MUSC usual care CMV protocol suggests measuring CMV DNA PCR in those that are D+/R- after prophylaxis is discontinued (post-transplant month 7, 9 and 12). The protocol also recommends measuring CMV DNA PCR at month 4, 7, and 12 after discontinuation of antiviral prophylaxis in moderate risk patients (R+, see Appendix). CMV symptoms and treatment will also be recorded. Late CMV infection will be defined based on occurrence of first CMV infection after completion of CMV prophylaxis (3- or 6-months post-transplant). These endpoints will be assessed at 3-, 6-, and 12-months post-transplant. Breakthrough cases of CMV infection, defined as the presence of CMV DNA while on anti-CMV prophylaxis, will also be assessed.
11. CMV Disease (Secondary Outcome) – defined as the presence of organ dysfunction in the setting of CMV infection with biopsy proven presence of CMV in the affected organ, done at MUSC using DNA hybridization. This will be sub-classified by organ type; most common in kidney transplant recipients will be CMV gastrointestinal disease, CMV pneumonia, or CMV nephritis. Less common include CMV hepatitis, CMV retinitis, CMV encephalitis, CMV cystitis, CMV myocarditis, and CMV pancreatitis. Late CMV disease will be defined based on occurrence of first CMV infection after completion of CMV prophylaxis (3- or 6-months post-transplant). This endpoint will be assessed at 3-, 6-, and 12-months post-transplant. Breakthrough cases of CMV disease will also be assessed.

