#### 10.0 Study Design / Methods

This will be a 12-month, single-center, open-label, randomized controlled clinical trial enrolling 70 total patients (35 in each arm). Given the limited sample size and single center design, this is a small, exploratory trial with limited power to detect significant differences between treatment arms for rates of CMV infection and other clinical endpoints (acute rejection, graft loss, death). The study is powered to detect clinically meaningful and statistically significant differences in the incidence of leukopenia accompanied by a reduce in total mycophenolate dose or valganciclovir dose (see power/sample size section). Patients will be randomly assigned to receive valganciclovir

900mg PO daily (this is considered standard usual care, adjusted for renal function) for 3-6 months post-transplant (based on CMV D/R serostatus as detailed below) or maribavir 400mg PO BID for 3-6 months post-transplant (based on CMV D/R serostatus as detailed below) + acyclovir 400mg PO BID for 1-month post-transplant (investigation arm, the addition of acyclovir to maribavir is considered standard usual care for HSV prophylaxis). Patients that are D+/R- will receive 6 months of prophylaxis, while all other CMV serostatuses will receive 3 months of prophylactic therapy (per MUSC usual care CMV protocol). All other medications, including immunosuppression and additional anti-infective prophylaxis, will be per standard usual care. All follow-up laboratory assessments and clinic visits will occur as per usual care as well. The only additional procedure specific to this study is that patients will be self-administered two surveys at 3, 6, and 12-months post-transplant, which can be completed online during a routine clinic visit or at home. There will be no visits conducted solely for this research study.

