### **Statistical Methods**

The analyses to assess for study Aims will be conducted using standard and widely accepted statistical methods. Data will be reported using percentages for nominal variables and univariate comparisons using Fisher's exact test or Pearson's chi-squared test as appropriate. This includes baseline demographics and transplant characteristics, as well as the non-time to event outcome

variables. For continuous variables with normal distribution, results will be reported using means and standard deviations with univariate statistical comparison using Student's t-test for two independent samples. For non-normally distributed variables, data will be reported using medians and interquartile ranges, with univariate statistical comparison conducted using the Mann Whitney U test. Normal distribution of continuous variables will be assessed using normality plots and the Shapiro-Wilk test. Normal variance will be assessed using Levene's test for equality of variances. Chi square or Fisher's exact test will be used for univariate assessments of key outcomes, including the incidence of leukopenia, neutropenia, CMV antiviral prophylaxis dosing interruption, CMV infection, acute rejection, graft loss and death.

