If necessary, multivariable analysis assessments for Aims 1 and 2 will be conducted using Cox regression time to event models. The primary variable of interest in these models will be treatment (maribavir vs. valganciclovir). If necessary and appropriate given event rates, Cox regression analysis will also be used for survival analyses involving all time to event outcomes, including time to acute rejection, time to graft loss and time to death. Models will be adjusted for key variables known to influence outcomes, including CMV serostatus and rATG induction. To prevent overfitting, no more than one covariate for every 5 events will be included in these models. Given the small sample size and expected event rates, Cox models will likely be overfit if including >2 covariates plus the primary treatment variable. Thus, multivariable modeling will be limited to only include key baseline variables that are known to influence the risk of CMV infection and that significantly differ by treatment arm based on preliminary univariate analyses; this will most likely only include CMV D+/R- serostatus and/or rATG induction. Prior to conducting Cox regression, modeling assumptions will be assessed, including proportionality of hazards across treatment arms and assessing the optimal functional forms of non-dichotomous covariates.

For Aim 3, total hospital charges and healthcare utilization will be modeled using a validated method we have used in previous studies. This will be a two-part statistical models for zero-heavy continuous data. The general format of the suggested model in which we fit a logistic model for the probability of non-zero response and a conditional generalized linear model (GLM) for the mean response given that it is non-zero. We will consider several distributions for the GLM part (eg, log-normal, gamma and Weibull, zero-inflated negative binomial [ZINB]) and the best fitting model will be selected using Bayesian information criterion (BIC). Parameter estimates of percent change in total hospital charge per unit increase in the values of each covariate in the model and their 95% CI will be computed using SAS Proc FMM.

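### Hypothesis 2 predicts similar CMV incidence, but the plan gives only tests of difference, with no margin, planned interval or rule for what would support similarity

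*Combined protocol and SAP*

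**What the plan says.** Section 1.0, Aim 2, is to assess efficacy. Its hypothesis is: "The incidence of CMV infection and disease will be similar between the maribavir arm, as compared to the valganciclovir arm", at 3, 6 and 12 months. Section 4.0 (Efficacy Measures, items 10 and 11) makes both secondary outcomes. Aims 4 and 5 are labelled exploratory in section 1.0; Aim 2 is not.

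The Statistical Methods part of section 10.0 gives two analyses that bear on this hypothesis:

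- "Chi square or Fisher's exact test will be used for univariate assessments of key outcomes", a list that includes CMV infection.
- "If necessary, multivariable analysis assessments for Aims 1 and 2 will be conducted using Cox regression time to event models", with treatment as the variable of interest.

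Neither comes with a non-inferiority or equivalence margin, a stated confidence interval for the CMV comparison, or a rule for what result would count as similar. The Power/Sample Size part concerns leukopenia only. Section 10.0 is open about the limitation: "this is a small, exploratory trial with limited power to detect significant differences between treatment arms for rates of CMV infection".

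**The concern.** A test of difference can give evidence against similarity but cannot, by itself, give evidence for it. If no other criterion is set, the only test result compatible with Hypothesis 2 is p>0.05, and a small trial makes that result more likely whatever the truth. Low power therefore favours the hypothesis.

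A leukopenia benefit can be interpreted only next to what happened to CMV protection. Section 16.0 presents similar efficacy and less leukopenia together as the expected benefit. Section 2.0 says adequately dosed randomized prophylaxis data in solid organ transplantation are lacking, so readers will look to this trial for an efficacy statement. Without an interval, a non-significant comparison could be over-read even when the data are compatible with a large excess of CMV infection on maribavir.

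**Working it through.** **The plan's own figure.** The only sample size is for leukopenia: 32 per arm for 33-35% versus 5-6%, raised to 35. For 33% versus 6%, the pooled-variance formula gives 33 per arm. The likelihood-ratio chi-square gives power 0.809 at 64 in total, which equals the table entry. That calculation is not in question. No power, sample size or margin is stated for CMV.

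**Inputs.**
- 35 per arm (section 6.0).
- Two-sided 0.05. The plan states this for the primary outcome; it is assumed here for CMV.
- Background rates from section 2.0: early infection 6% (95% CI 1 to 31%), late infection 17% (2 to 29%), and 12-month disease 16.1% in D+/R- patients given 200 days of valganciclovir.
- Two higher valganciclovir rates, assumed to show the range: 23% (6% + 17%, simply added) and 29% (upper limit of the late-infection interval).

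**Step 1: chance of missing a doubling.** Power is the sum, over all pairs (a, b) of event counts with p≤0.05, of Bin(a; 35, p) × Bin(b; 35, 2p).

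| Valganciclovir → maribavir | Power, Pearson | Power, Fisher | Missed, Pearson / Fisher |
|---|---|---|---|
| 6% → 12% | 0.15 | 0.047 | 85% / 95% |
| 16.1% → 32.2% | 0.34 | 0.26 | 66% / 74% |
| 17% → 34% | 0.367 | 0.277 | 63% / 72% |
| 23% → 46% | 0.54 | 0.44 | 46% / 56% |
| 29% → 58% | 0.68 | 0.60 | 32% / 40% |

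The plan leaves the choice between the two tests open. If Fisher is used only when an expected count is below 5, power at 6% → 12% is 0.057 (missed 94%). At 17% → 34% it stays at 0.367.

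**Step 2: precision when the arms are truly equal.** The 95% half-width is 1.96 × √(2p(1−p)/35). At 17%: 1.96 × √(2 × 0.17 × 0.83/35) = 1.96 × 0.0898 = 0.176, or ±17.6 points.

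**Step 3: the excess that could be excluded with 80% power, arms truly equal.** This is (1.96 + 0.84) × √(2p(1−p)/35):
- 6%: 2.80 × 0.0568 = 0.159, about 16 points
- 17%: 2.80 × 0.0898 = 0.251, about 25 points
- 29%: 2.80 × 0.1085 = 0.304, about 30 points

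The normal approximation is rough at 6%, where about 2 events per arm are expected (35 × 0.06 = 2.1).

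**Step 4: an example.** With 6/35 on valganciclovir and 12/35 on maribavir, chi-square p=0.10 and Fisher p=0.17. The difference is 17.1 points, with a Newcombe 95% interval of about −3 to +36 points. The observed rate has doubled, the test is non-significant, and the interval shows how little has been ruled out.

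**The case against.** The strongest reply is that the plan is candid. It calls the trial small and exploratory, concedes limited power for CMV infection, makes the endpoint secondary, and powers the study for leukopenia. Section 15.0 says relative efficacy in prophylaxis is unproven, and section 16.0 speaks only of a strong possibility. Cox regression, if used, would yield an effect estimate. All of this stands and lowers the seriousness. It does not close the gap: the power statement neither amends Hypothesis 2 nor says how a null result will be interpreted, and the Cox model is conditional, with no interval or margin specified for it.

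Three stronger readings are tempting and should not be adopted:

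- *That the sponsor will declare similar efficacy from p>0.05.* No section says so. It is an inference from the absence of any other criterion.
- *That a doubling of CMV infection would usually be missed whatever the rate.* This holds at the 6%, 16.1% and 17% rates. At 23% it holds with Fisher (56%) but not with Pearson (46%), and at 29% with neither. The 17% is a late-infection rate from a review of kidney recipients, whereas Hypothesis 2 covers all infection by each time point in a high-risk group.
- *That 25 points is the difference this trial can exclude.* It is the value at one background rate; Step 3 gives about 16 to 30 points over 6% to 29%.

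**Conclusion.** The mismatch is real: a hypothesis of similarity is paired with analyses that can only detect a difference, and nothing defines what would support it. It concerns the wording and reporting of a secondary aim. It does not touch the primary analysis or its sample size.

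The size depends on the CMV rate on valganciclovir and on the test chosen. The share of trials in which a doubling is non-significant runs from about 85-95% at 6%, through 63-72% at 17%, to 32-40% at 29%. These figures assume 35 evaluable patients per arm and two-sided 0.05. The expected 3-5% dropout would make them slightly worse. The disclosure of limited power does not cure the problem, because low power makes the result compatible with the hypothesis more likely.

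**What to change.** - Reword Hypothesis 2 as estimation: the between-arm differences in CMV infection and in CMV disease will be estimated at 3, 6 and 12 months.
- In Statistical Methods, add the difference in proportions with a 95% confidence interval (for example Newcombe) at each time point, alongside any chi-square or Fisher test. If Cox regression is used, report the hazard ratio with its 95% interval.
- State that a non-significant p-value will not be described as similar efficacy, and that conclusions will rest on the differences the interval excludes.
- Do not write a fixed excludable difference, such as 25 points, into the protocol, because it depends on the observed rate.

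If the sponsor prefers to keep a formal similarity claim, it needs a justified margin, and 70 patients will not support a narrow one. For an assumed 17% in both arms and one-sided 0.025, non-inferiority power at 35 per arm is about 60% for an assumed 20-point margin and 20% for an assumed 10-point margin.

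The estimation route needs no extra patients, visits or data. Its cost is a few sentences, a few intervals and a more modest efficacy claim. It should be settled before outcome data are analysed.

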## 2.0 Background

Despite substantial advances in screening, monitoring, therapeutics and management, CMV infection remains a significant problem in kidney transplantation and CMV is still considered by clinicians to be the most important post-transplant infection. Although universal prophylaxis with potent antiviral therapy has significantly reduced the risk of early CMV infection and disease ( $\leq 6$  months), late onset CMV ( $> 6$  months post-transplant) is still quite common and can be difficult to clinically manage, particularly in high-risk patients, including those receiving rabbit antithymocyte globulin (rATG) induction and those that are sero mismatched (D+/R-). A recent systematic review demonstrated that with antiviral prophylaxis, early CMV infection occurred in only 6% (95% CI 1 to 31%) of kidney transplant recipients, while late infection occurred in more than one in six patients (17%, 95% CI 2 to 29%). The results of the IMPACT study, a randomized controlled trial comparing 100-days to 200-days of oral valganciclovir therapy in D+/R- patients highlights the continued issue of late CMV infection. Although patients randomized to the 200-days of therapy had a significant reduction in CMV disease, rates were still quite high. The 12-month incidence of CMV disease was 16.1% in these patients, despite receiving more than 6-months of valganciclovir prophylaxis.

Valganciclovir antiviral prophylaxis is highly effective at preventing CMV infection, but it has numerous limitations. Of particular concern is the high rates of cytopenias; most notably, leukopenia and neutropenia. This often leads to a clinical conundrum, whereby it is unclear if the low WBC count is due to valganciclovir therapy itself, a breakthrough CMV infection, or mycophenolate therapy. Oftentimes, this clinical dilemma causes multiple additional laboratory interrogations, reductions in full dose valganciclovir and/or mycophenolate therapies, and in severe cases, the administration of filgrastim (Neupogen®, G-CSF). In studies using valganciclovir for CMV prevention, the reported the incidence of post-kidney transplant leukopenia is 20 to 40% and neutropenia is upwards of 10% at 30%.

Maribavir has been evaluated for the prevention of CMV infection in phase II and phase III trials within allogeneic stem cell transplant recipients. At 6-months post-transplant, the rates of CMV infection using PCR were not different between treatment and placebo arms, although the rates of pp65 antigenemia were lower in the maribavir group. However, these studies used a low dose of 100mg PO BID. In subsequent studies within solid organ transplantation, maribavir dosed at 400 to 1200mg PO BID was equally efficacious to valganciclovir for the treatment of CMV infection. Of note and importance to this proposal, the rates of neutropenia were 4-5% in the maribavir treated patients vs. 15-18% in valganciclovir patients. Thus, at an appropriate dose, maribavir appears to have similar efficacy to valganciclovir in treating CMV infection with a significantly reduced incidence of neutropenia. Currently, there is a lack of randomized controlled trials assessing the safety and efficacy of adequately dosed ( $\geq 400$ mg PO BID) maribavir for the prevention of CMV infection in solid organ transplant recipients.

### 3.0 Intervention

Patients will be randomized to receive either maribavir 400mg PO BID or valganciclovir 900mg daily (standard of care dose, adjusted for renal function) for CMV prophylaxis for 3 to 6 months post-transplant. Those that are CMV serostatus D+/R- will receive 6 months of antiviral therapy; all others will receive 3-months of therapy. The current gold-standard therapy is valganciclovir for 3- to 6-months of therapy. Those randomized to maribavir will also receive 1-month of acyclovir 400mg PO BID for HSV prophylaxis (standard of care dose). Beyond these interventions, all follow-up care and laboratory monitoring will be conducted as per usual care protocols. All immunosuppression will be given and dosed as per usual care protocols. There will be no additional visits or laboratory measurements as part of this study.

### 4.0 Study Endpoints

#### Safety Measures

1. Leukopenia with an accompanying dose reduction (Primary Outcome) – Defined as a total WBC count of  $< 3,000$  cells/mm^3 with a reduction in the total daily dose of mycophenolate below 1500mg per day or valganciclovir below 900mg daily (adjusted for renal function). This will be assessed as a dichotomous outcome (yes/no) per patient as well as a rate (number of unique leukopenia events per patient-year). Events will be considered unique once the WBC count recovers to normal range on two consecutive measures. The length of time a patient has leukopenia, and the severity of leukopenia (nadir WBC) will also be assessed. This endpoint will be measured at 3-, 6-, and 12-months post-transplant.

2. Neutropenia (Secondary Outcome) – Defined as an absolute neutrophil count of  $<1,000$  cells/mm^3. This will be assessed as a dichotomous outcome (yes/no) per patient as well as a rate (number of unique neutropenic events per patient-year). Events will be considered unique once the neutrophil count recovers to normal range on two consecutive measures while not receiving G-CSF therapy. The length of time a patient has neutropenia, and the severity of leukopenia (nadir WBC) will also be assessed. This endpoint will be measures at 3-, 6-, and 12-months post-transplant.
3. Mycophenolate mofetil dose reduction (Secondary Outcome) – Defined as a reduction in dose of  $<1,500$  mg per day ( $<750$  mg PO BID). This will be assessed as a dichotomous outcome (yes/no) per patient as well as a rate (number of unique mycophenolate dose reduction events per patient-year). Events will be considered unique once the mycophenolate dose is returned to full dose for at least one week. The length of time a patient has their mycophenolate dose  $<1,500$  mg per day and the severity of mycophenolate dose reduction (nadir dose) will also be assessed. This endpoint will be measures at 3-, 6-, and 12-months post-transplant.
4. Valganciclovir dose reduction (Secondary Outcome) – Defined as a reduction in dose of  $<900$ mg per day (adjusted for renal function. This will be assessed as a dichotomous outcome (yes/no) per patient as well as a rate (number of unique valganciclovir dose reduction events per patient-year). Events will be considered unique once the valganciclovir dose is returned to full dose for at least one week. The length of time a patient has their valganciclovir dose reduced and the severity of dose reduction (nadir dose) will also be assessed. This endpoint will be measures at 3-, 6-, and 12-months post-transplant.
5. CMV prophylaxis drug dose adjustment or discontinuation (Secondary Outcome) – Defined as a reduction in dose, holding or discontinuation of the maribavir or valganciclovir therapy. This will be assessed as a dichotomous outcome (yes/no) per patient as well as a rate (number of unique dose adjustment events per patient-year). Events will be considered unique once the CMV prophylaxis drug dose is returned to full dose for at least one week. The length of time a patient has their CMV prophylaxis drug dose reduced or held and the severity of dose reduction (nadir dose) will also be assessed. This endpoint will be measures at 3- and 6-months post-transplant.
6. Acute Rejection (Secondary Outcome) - defined as a renal allograft biopsy demonstrating at least grade 1A rejection by Banff criteria. We will also record and assess all borderline acute rejections and antibody mediated rejections using the most current Banff classification system. All patients will be required to have biopsy confirmation of rejection episodes, as per usual care and the MUSC clinical protocol. It is standard care that all kidney allograft biopsies performed for transplant recipients occur at the transplant center (study institution). Biopsies will be read by the local pathologist, as usual care. The study coordinator capturing clinical event data will review the medical record to determine the timing, severity, treatment regimen and reversibility of each acute rejection episode for all patients in the study.
7. Hospitalizations (Secondary Outcome) – Defined as any admission to a hospital with at least one overnight stay. All-cause hospitalization will be assessed for this study. Hospitalizations due to CMV and other infections will be sub-analyzed as well.
8. ED Visits (Secondary Outcome) – Defined as any visit to the emergency room for any cause during the post-transplant period. We will collect the cause and date of the ED visit as well. ED visits due to CMV and other infections will be sub-analyzed as well.

9. Graft function, Graft Failure and Death (Exploratory Outcome) – graft function will be defined using the 4-variable MDRD equation to estimate GFR. This equation has been validated as an accurate reflection of true GFR within kidney transplant recipients. Routine serum creatinine concentrations, which are measured as part of usual care, will be utilized to estimate GFR and aggregated at 3-, 6- and 12-months post-transplant. Graft failure will be defined as return to chronic dialysis, nephrectomy, retransplantation or death. The study coordinator capturing clinical event data will review the medical record at regular intervals to determine if a study patient has developed graft failure. The timing and cause of each graft loss will be recorded for comparative analysis. Patient death will also be captured in a similar fashion, with timing and cause recorded as well.

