### 3. Recipient of investigational, non-FDA approved medication

#### 6.0 Number of Subjects

70 patients will be randomized 1:1 (35 in each arm) in blocks of 10. Once a patient is randomized and receives at least one dose of CMV prophylaxis medication they will be included in the study in an intent-to-treat manner. Those that are lost to follow-up, withdraw, or are taken off study drug will not be replaced.

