The incidence of clinically significant leukopenia (WBC <3K AND dose reduction in MMF) is difficult to assess in the maribavir arm, as this specific issue is not reported in the published data. However, there are several studies that can be used to estimate this incidence for power/sample size purposes. In a study conducted in liver transplant patients, known to be at higher risk for cytopenias than kidney recipients, the incidence of neutropenia was 6% in the maribavir arm (Winston DJ et al Am J Transplant 2012;12:3021-30.). In a phase III prophylaxis study in allogeneic stem-cell transplants, who are very high risk for cytopenias, the incidence of neutropenia was similar between the maribavir, and placebo arms and the average WBC count was 4.2K in the placebo arm and 4.4K in the maribavir arm (Papanicolaou GA et al. Clin Inf Diseases 2019;68:1255-64.). Thus, maribavir does not appear to induce or worsen leukopenia and a 5% incidence is a reasonable expectation in the maribavir treatment arm for estimating sample size and power.

To meet at least 80% power, given an incident rate of 33 to 35% in the valganciclovir arm and 5 to 6% in the maribavir arm, 32 patients in each arm is required, assuming two independent samples, a two sided  $\alpha=0.05$ , and using the chi square test. This sample-size will be inflated to 35 patients per arm to address an expected dropout/lost to follow-up rate of 3-5% in each arm. Thus, 70 total patients, 35 in each arm, will provide adequate power to assess the primary aim of this study. SAS 9.4 (SAS Institute, Cary, NC) was utilized to conduct sample-size estimations (Proc Power).

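### The primary endpoint counts valganciclovir cuts but not maribavir cuts, so it can favour maribavir at equal leukopenia, by an amount the documents do not let us fix

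*Combined protocol and SAP*

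**What the plan says.** Section 4.0 (Safety Measures, item 1) defines the primary outcome as a WBC count under 3,000 "with a reduction in the total daily dose of mycophenolate below 1500mg per day or valganciclovir below 900mg daily (adjusted for renal function". Hypothesis 1 in section 1.0 uses the same two-drug condition: "and a reduction in total mycophenolate dose below 1,500 mg/day or valganciclovir dose below 900mg per day (adjusted for renal function". Neither place mentions a change to maribavir.

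Section 3.0 gives each patient one drug or the other: "Patients will be randomized to receive either maribavir 400mg PO BID or valganciclovir 900mg daily". Section 10.0 describes a "12-month, single-center, open-label, randomized controlled clinical trial enrolling 70 total patients (35 in each arm", with dosing and monitoring left to usual care.

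The plan does have a construct that covers both study drugs, but only as a secondary outcome. Item 5 is "Defined as a reduction in dose, holding or discontinuation of the maribavir or valganciclovir therapy".

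The Power/Sample Size text is not uniform. Its opening paragraph defines the event with a mycophenolate or valganciclovir cut. The supporting table counts mycophenolate (MMF) cuts only. The next paragraph uses the narrower form again: "The incidence of clinically significant leukopenia (WBC <3K AND dose reduction in MMF) is difficult to assess in the maribavir arm".

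**The concern.** Take two patients with the same low WBC count whose clinician responds by changing the antiviral and leaving mycophenolate alone. On valganciclovir that is a primary event; on maribavir it is not. The control arm can reach the event by two routes and the maribavir arm, on its assigned drugs, by one.

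This is the only endpoint the trial is powered for, and it carries the main claim. If the extra route is used often, part of an observed difference would come from the definition and not from less leukopenia. No WBC-only incidence and no symmetric composite is prespecified that would separate the two.

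**Working it through.** **The plan's own figure.** Using the likelihood-ratio chi-square approximation with H(p) = p ln p + (1−p) ln(1−p):

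δ = √(2N[½H(p₁) + ½H(p₂) − H(p̄)]), power = Φ(δ − 1.960).

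For 33% against 6% with N=64: H(0.33) = −0.6342, H(0.06) = −0.2270, H(0.195) = −0.4934. The bracket is 0.0628, δ = √(128 × 0.0628) = 2.836, and power = Φ(0.876) = 0.809, as printed. The same formula returns the printed total in 16 of the 17 scenarios; the exception is 31% against 5%, where 61 is printed and the formula gives 64. The sample-size arithmetic is not at issue here.

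**Inputs for the bias check.**
- rATG rows of the internal table (Power/Sample Size): WBC <3K 56.7%; WBC <3K with MMF cut 34.6%.
- Leukopenic without an MMF cut: 56.7 − 34.6 = 22.1%.
- 35 per arm (section 6.0: "70 patients will be randomized 1:1 (35 in each arm) in blocks of 10"), two-sided 0.05, chi-square or Fisher (Statistical Methods).
- x, the share of that 22.1% who have valganciclovir cut in the control arm. The documents do not give it, so it is an assumption, ranged from 0 to 100%.
- y, the share of the 22.1% in the maribavir arm who have mycophenolate cut because valganciclovir is not there to cut. Also not given, and set to 0 at first.

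**Formula.** Leukopenia is identical in both arms. Control event rate = 34.6 + 22.1x; maribavir event rate = 34.6 + 22.1y. The chance of p<0.05 is summed exactly over all pairs of binomial outcomes at 35 per arm.

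**Results with y=0 (maribavir arm 34.6%).**

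| x | Control arm | Spurious gap (points) | Pearson, two-sided | Fisher, two-sided |
|---|---|---|---|---|
| 0 | 34.6% | 0 | 5.2% | 2.9% |
| 25% | 40.1% | 5.5 | 7.7% | 4.8% |
| 50% | 45.7% | 11.1 | 15.2% | 10.4% |
| 75% | 51.2% | 16.6 | 27.5% | 20.5% |
| 100% | 56.7% | 22.1 | 44.0% | 35.1% |

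From x=50% upward nearly all of this error favours maribavir (15.0 of the 15.2 points at x=50%).

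**Results with y above 0.** At x=50%, y=25% the rates are 45.7% and 40.1%, and the Pearson false-positive rate is 6.9%. At x=100%, y=50% they are 56.7% and 45.7%, and it is 13.7%. When y=x the gap is zero.

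**The opposite tilt.** Suppose control-arm clinicians cut valganciclovir in place of mycophenolate for a quarter of those who would otherwise have had an MMF cut. A mycophenolate-only endpoint would then show 34.6 × 0.75 = 26.0% against 34.6%, with a 12.1% chance of a significant result against maribavir.

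**Planning rates.** The 33–35% control rate rests on the 34.6% in a table that does not count valganciclovir cuts. Under the declared endpoint the same data would give 34.6 + 22.1x, so 34.6% or more.

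**The case against.** The strongest reply is that the two drugs are alternative levers. Section 2.0 says a low count may lead to a cut in either or both. In the maribavir arm mycophenolate is the main lever left, so MMF cuts may be more frequent there, and naming valganciclovir in the endpoint can be read as a correction for this. That stands: the direction and size depend on x and y, neither of which is documented, and an MMF-only endpoint could be biased the other way. It does not make the declared definition even-handed; it means that any balance would be accidental.

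Two further points stand in part. The 56.7% and 34.6% are one-year rates, whereas valganciclovir is given for 3 or 6 months, so leukopenia arising after prophylaxis ends cannot use the extra route, and x=100% is an extreme bound. And MMF reduction, valganciclovir reduction, changes to either study drug, neutropenia, nadir WBC and duration of leukopenia are all prespecified, so a reader could partly see what drives the result. WBC <3,000 incidence by arm is still missing from that list.

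Valganciclovir cuts are arguably a real harm of that drug. A symmetric definition still counts them.

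Some stronger inferences are tempting but not supported:
- That only control patients could ever qualify by this route. The definition is not limited to assigned prophylaxis, so a maribavir patient later given valganciclovir might qualify.
- That the 5% maribavir rate is itself a mycophenolate-only figure. The Power/Sample Size text says the combined event is unreported for maribavir and infers 5% from neutropenia and WBC data.
- That item 5 necessarily counts routine renal adjustment of valganciclovir as an event. It lacks the qualifier found in items 1 and 4, but section 3.0 defines the assigned dose as renally adjusted, and a reduction can be read against that dose.

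**Conclusion.** The concern holds as an asymmetry of definition with an unknown and possibly offset effect. In an open-label trial the control arm has an additional, clinician-driven route to the primary event. With equal leukopenia and equal MMF cuts, the Pearson false-positive rate rises from 5.2% to 7.7% at x=25% and 15.2% at x=50%, with 44.0% as an outer bound. It falls back to 6.9% if y=25% at x=50%, and there is no inflation if y=x.

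A reader might infer that a significant primary result would be an artefact. The documents do not support that. The largest gap in this calculation is 22.1 points, below the planned difference of 27 to 30 points (33−6 and 35−5), so the definition could inflate an effect but would not on these figures create all of it.

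Separately, the control planning rate describes a narrower event than the one declared. This needs correcting whatever view is taken of the bias.

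**What to change.** 1. Make the dose component symmetric: count a reduction, hold or discontinuation of the assigned CMV prophylaxis drug in either arm, excluding renal-function adjustment and scheduled completion.
2. Prespecify the incidence of WBC <3,000 alone, by arm, as the key secondary check, and require the primary result to be interpreted beside it. This is the main safeguard: if clinicians rarely change maribavir for leukopenia, step 1 alone may leave most of the gap.
3. Report WBC <3,000 with a mycophenolate cut as a sensitivity analysis, noting that it may tilt against maribavir if valganciclovir is cut in place of mycophenolate.
4. Reconcile the endpoint definition across section 4.0 item 1 and the Power/Sample Size text, and state that the control planning rate is mycophenolate-only.
5. Report item 4 (valganciclovir dose reduction) descriptively for the valganciclovir arm, not as a between-arm comparison.

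Cost: outcome and analysis wording; antiviral doses, immunosuppressant doses and blood counts are already collected. The observed difference may shrink, and the symmetric composite has no direct planning rate in either arm. The WBC-only check may also be underpowered. The documents give no maribavir rate for it; assuming 20%, 25%, 30% or 36.7% against 56.7%, power at 35 per arm (pooled Pearson approximation) is 0.90, 0.78, 0.62 or 0.39. It should be read with its confidence interval, not as a pass-or-fail test.
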